- Organic lesion at risk of bleeding
- Spontaneous or pharmacological impairment of haemostasis

- Hepatic impairment or liver disease expected to have any impact on survival
- Concomitant treatment with systemic ketoconazole, cyclosporine, itraconazole, and tacrolimus

The contraindications have been updated since August 2011, and the following contraindication(s) are approved in the current EU label for Pradaxa:

- Hypersensitivity to the active substance or to any of the excipients
- Patients with severe renal impairment (creatinine clearance < 30 mL/min)
- Active clinically significant bleeding
- Lesion or condition, if considered a significant risk factor for major bleeding. This may include current or recent gastrointestinal ulceration; presence of malignant neoplasms at high risk of bleeding; recent brain or spinal injury; recent brain, spinal, or ophthalmic surgery; recent intracranial haemorrhage; known or suspected oesophageal varices; arteriovenous malformations; and vascular aneurysms or major intraspinal or intracerebral vascular abnormalities (contraindication extended since June 2012)
- Concomitant treatment with any other anticoagulants, e.g., unfractionated heparin (UFH), low-molecular-weight heparins (enoxaparin, dalteparin, etc.), heparin derivatives (fondaparinux etc.), oral anticoagulants (warfarin, rivaroxaban, apixaban, etc.), except under the circumstances of switching therapy to or from Pradaxa or when UFH is given at doses necessary to maintain an open central venous or arterial catheter (contraindication added since June 2012)
- Hepatic impairment or liver disease expected to have any impact on survival
- Concomitant treatment with systemic ketoconazole, cyclosporine, itraconazole, tacrolimus (tacrolimus contraindication deleted since December 2013), or dronedarone (use of dronedarone contraindicated since August 2012)
- Prosthetic heart valves requiring anticoagulant treatment (since January 2013)

As a regulatory pharmacovigilance commitment, the EMA requested Boehringer Ingelheim International GmbH (BI) to provide a study protocol for “a study to assess potential off-label use [of the medication] outside of atrial fibrillation (AF).” The study protocol was originally submitted to the EMA in August 2011, and a CHMP opinion was finally adopted October 2012. The protocol is proposed to be revised to include several label updates and revised target countries based on reimbursement and medication uptake.

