The Cegedim panel of participating medical doctors is selected from a large number of French physicians who use the Cegedim management software for their daily practice. These office-based, active physicians have agreed to upload to CSD servers anonymous and coded excerpts from medical files of patients who have come to see them. The data collected are gathered for each patient within the same doctor's office, thus providing longitudinal data on the same patients. The representativeness of the panel of physicians is checked using three criteria known to influence prescribing: age, sex, and geographic area of coverage. However, there are limitations in this database such as no availability of information on hospitalisations, deaths, or date transferred out of the system. Data from panels of primary care physicians and data from specialist panels are available. Panels of specialists are independent of GP panels; therefore, an overlap between patients included in primary health practices and in those from specialists could occur but it is not possible to link individual patients across the two types of practitioners. For this study, it is planned to include also information gathered by cardiologists due to the potential that the first prescription of Pradaxa will be issued by these specialists. Therefore, all the information should be stratified by the type of panel and clinical specialty. Oral anticoagulants are expected to be recorded completely when prescribed by the physicians participating in the panel; however, the first prescription can be missed if issued in the hospital or outside of the participating physicians.

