
Database type
 
Database population²
 
Approximate proportion of the country's population covered by the database
 
Potential number of dabigatran etexilate users in 2012 captured in the database (based on BI sales estimates)
	
Primary health care electronic medical record database plus linkage to HES and other data
 
5.1 million
 
8%
 
8,000
	
National health record databases capable of linkage with other databases though the unique personal number assigned by the Central Person Registry
 
5.6 million
 
100%
 
15,000
	
Primary health care electronic medical record database
 
2.6 million
 
4%
 
4,000

Data on medications
 
Dose
 
Duration
	
GP prescriptions
 
Prescribed dose
 
As indicated by the written prescription
	
Pharmacy-dispensed prescriptions, reimbursed and unreimbursed.
 
Formulation strength
 
Based on dispensed prescriptions
	
GP prescriptions and Cardiologists prescription
 
Prescribed dose
 
As indicated by the written prescription

Table 1 (cont'd) Characteristics of automated primary health care databases available in the UK, Denmark, and France

Clinical indication	Associated with new courses of medications, but completeness is variable. Computerised free-text information is available for review.	Not specifically recorded but based on proxies	Associated with new courses of medications, but completeness is variable
Outpatient diagnosis	Yes (Read codes)	Only outpatient hospital diagnosis in the patient register (ICD-10-CM); primary care diagnoses in DAMD (ICPC codes)	Yes (ICD-10-CM)
Hospital diagnosis	Recorded by GPs and partial linkage to HES (Read and ICD-10-CM)	Yes (ICD-10-CM)	No
Access to medical records	GPs, and partial linkage to HES	Partial access to hospitals, only in some regions	No
Prior atrial fibrillation assessment	Yes, based on recorded Read codes and validated through GP survey [R10-0421]	Yes (AF diagnosis with positive predictive value of 93%) [R13-5417]	Yes, based on recorded information, but unpublished [R11-4018]
Lifestyle risk factors	Yes	Yes, in DAMD	Yes
Data availability	Since 1987	Since 1994	Since 1994
Updates	At 3- to 4-month intervals	Yearly	Monthly
Approximate time lag	6-12 weeks	2012 data available in 3-4Q 2013	2-7 months

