3.5.1 On-label use definition

On-label use is when a medication is used as described in the approved drug label. As of 1 August 2011, the EMA-approved indications for Pradaxa were as follows:

- Primary prevention of venous thromboembolic events in adult patients who have undergone elective total hip replacement surgery or total knee replacement surgery.
- Prevention of stroke and systemic embolism in adult patients with non-valvular atrial fibrillation with one or more of the following risk factors:
 - Previous stroke, transient ischaemic attack, or systemic embolism (SEE)

- Left ventricular ejection fraction < 40%
- Symptomatic heart failure, New York Heart Association (NYHA) Class 2 or higher
- Age \geq 75 years
- Age \geq 65 years associated with one of the following: diabetes mellitus, coronary artery disease, or hypertension

A revision of this indication statement was submitted for approval in the EU in September 2013. The revision became effective in December 2013, introducing the following modified indication statement: “Prevention of stroke and systemic embolism in adult patients with non-valvular atrial fibrillation (NVAF) with one or more risk factors, such as prior stroke or transient ischemic attack (TIA); age \geq 75 years; heart failure (NYHA Class \geq II); diabetes mellitus; hypertension.”

The indication application for treatment or secondary prevention of venous thromboembolism EMA/H/C/00829/II/48G obtained a positive CHMP opinion on 25 April 2014 with the following indication statement: “Treatment of deep vein thrombosis (DVT) and pulmonary embolism (PE), and prevention of recurrent DVT and PE in adults.” During the study period, use associated with these indications will be considered off-label use until Commission Decision. The definition of on-label use will have to consider regulatory label changes that have occurred during the product life cycle with respect to indication and also to contraindications (e.g., addition of dronedarone use to the list of contraindications since 30 August 2012). Therefore on-label use will be defined considering the index date and the appropriate label indication and contraindication applicable during the time period comprising the index date.

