3.5.2 Off-label use definition

The definition of off-label use of oral dabigatran etexilate outside AF will be based on the use for a disease or medical condition other than the labelled indications and patient sub-groups given in Section [3.5.1](#). The dabigatran indications approved at the time of the index date will be used to define off-label use for each new user identified in the study period. In the absence of labelled indications, potential off-label use could include, but is not limited to, the following:

- General thrombosis prophylaxis other than hip and knee orthopaedic surgery.
- Treatment of deep vein thrombosis (DVT) and pulmonary embolism (PE) and prevention of recurrent DVT and PE in adults (CHMP opinion 25 April 2014), until Commission Decision
- Anticoagulation for patients with heart valve replacement or a stent.
- General prophylaxis or treatment of a thrombus in any site.
- Patients with hypercoagulability (e.g., factor V Leiden thrombophilia).

A preliminary list of ICD-10-CM codes to identify these conditions is provided in [Table 5](#). The final list will be included in the detailed, database-specific study protocol. In addition, the set of algorithms to be used as proxies for identification of potential clinical indications will be defined and described in the detailed, database-specific study protocol. These proxies will be based on codes for the presence of certain diseases and clinical conditions and the use of certain medications (e.g., use of other oral anticoagulants).

Because dabigatran etexilate has been approved for use only in adults, any identified use in the pediatric groups of age will be considered off-label. New users of dabigatran etexilate aged younger than 18 years at the index date will be considered in the pediatric population.

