The proportion of users with each of the contraindications, including those based on comedication, disease, or severity of conditions, such as patients with severe renal impairment, will be also described. In those databases with laboratory test results available, severe renal impairment will be defined as creatinine clearance < 30 mL/min from directly recorded information of the estimated renal function, as available. For those patients with serum creatinine levels and patient weight available, we might estimate glomerular filtration rate by using the Cockcroft-Gault equation and/or the CKD-EPI equation [[R13-5416](#)]. However, it is important to be aware that actual values of laboratory test results will be inconsistently recorded in most databases and data will be limited. We will also capture those patients with ICD-10-CM codes for advanced renal disease—N18.4-N18.6, chronic kidney disease, stages 4 and 5 (severe), and end-stage renal disease—as available in each database according to the coding system and version in place.

Given the different recommended dosage regimens in both the approved and the new indications, new users of dabigatran etexilate will be described according to dose categories, but dose will not be included in the study definition of off-label use based on the first level of on-label indications.

Dose will be incorporated in the definition of off-label use based on the second level, which is a more restrictive definition of on-label use (see [Appendix 4](#)). In addition, the proportion of new users within the primary VTE prevention subgroup with one or more follow-up prescriptions after the recommended treatment duration will be described. The follow-up prescriptions will be assessed in the 90-day time window after the index prescription..

Table 5 Preliminary list of diagnoses and corresponding ICD-10-CM codes for identification of potential off-label clinical indications of dabigatran etexilate

Disease/condition or procedure	ICD-10-CM description	ICD-10-CM code	Use of codes in off-label indication definitions
Treatment or secondary prevention of venous thromboembolism	Venous thrombosis Pulmonary embolism	I80.1*, I80.2*, I82.3* I26*	
General thrombosis prophylaxis other than hip and knee orthopaedic surgery	Injuries to the knee and lower leg Fracture of femur	S80*-S89* S72*	In the absence of codes for hip or knee orthopaedic surgery (see Table 3)

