3.7.1 Main analysis by indication

The main analysis will be to estimate (with 95% confidence intervals) the prevalence proportion of off-label use among new users of dabigatran etexilate during the overall study period in each of the study populations. This will include potential off-label clinical indications and contraindications. The proportion of each of the most common off-label use indications will be described among the overall off-label use group. The proportion of identified users in the pediatric age subgroup will be described.

In addition, separately for each approved clinical indication, the risk profile and use of selected drugs among new users of dabigatran etexilate will be described.

The distribution of the dispensed formulation strength or the daily prescribed dose at the index date based on the index prescription will be described, overall and by on-label and off-label indication sub-group. The proportion of new users within the primary VTE prevention subgroup with one or more follow-up prescriptions after the recommended treatment duration will be described. The follow-up prescriptions will be assessed in the 90-day time window after the index prescription.

To evaluate the differences between sub-groups by indication, proportions for categorical variables and means for continuous variables will be estimated (with 95% confidence intervals) within each sub-group. If appropriate, medians will be used instead of means when the variables of interest do not assume a normal distribution.

All the results will be presented for each country-specific database. In addition, for France, all the data will be stratified by type of physician panel: primary care or cardiologist. As part of the analysis, tables presenting the results will be generated. Table shells for the key descriptive analyses will be developed for the detailed, database-specific protocol.

A weighted, pooled prevalence of off-label use among new users of dabigatran etexilate for the entire study population (CPRD, Cegedim, and Danish national databases) will be estimated (with 95% confidence intervals) when the individual results of all three databases are available.

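### Contraindications count toward the main off-label figure without regard to whether each database can observe them; in Cegedim those diagnosed in hospital or created by another prescriber will be under-counted

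*Protocol*

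**What the plan says.** **What is reported.** Protocol section 3.5.2 plans to describe "The proportion of users with each of the contraindications, including those based on comedication, disease, or severity of conditions". Availability qualifiers appear there only for renal impairment (laboratory values and renal disease codes).

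**Whether it enters the main outcome.** The sections differ:
- 3.5.2 defines off-label use by indication: it "will be based on the use for a disease or medical condition other than the labelled indications and patient sub-groups". Contraindications are described in addition.
- 3.5.1 says that "on-label use will be defined considering the index date and the appropriate label indication and contraindication applicable" at that time.
- 3.7.1 says of the main off-label prevalence: "This will include potential off-label clinical indications and contraindications".
- 3.7.1 then plans a weighted, pooled off-label prevalence over the three databases. It does not say whether contraindications are part of it.

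**Which conditions are affected.** The current contraindications listed in section 1 include "recent brain, spinal, or ophthalmic surgery; recent intracranial haemorrhage", recent brain or spinal injury, active clinically significant bleeding, and several interacting drugs.

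**What each database can see.**
- Cegedim (3.1.2): "there are limitations in this database such as no availability of information on hospitalisations, deaths, or date transferred out of the system". Of the GP and specialist panels, the section says "it is not possible to link individual patients across the two types of practitioners". Table 1 answers No for hospital diagnosis.
- Denmark (3.1.3, Table 1): a national register of all admissions since 1977 and of outpatient-clinic and emergency visits since 1995, plus pharmacy dispensing. Primary-care diagnoses come only from DAMD, which covered about 1 million people in 2012.
- CPRD (Table 1): hospital diagnoses are "Recorded by GPs and partial linkage to HES (Read and ICD-10-CM"). Section 3.1.1 adds free text and letters from specialists and hospitals.

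**The concern.** Several listed contraindications are events normally diagnosed or treated in hospital. If a database holds no hospital records, a user with such an event is not flagged as missing. The user is simply classified as not having the contraindication. The same holds for an interacting drug prescribed outside the panel doctor's office. One table row would then mean different things in France and in Denmark.

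At stake is a reassuring artefact: a low French figure for contraindicated use could be read as a difference in prescribing when it reflects what the data can show. The planned 95% confidence intervals cover sampling error only and would not warn the reader.

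**Working it through.** **1. The plan's own precision figure.** Table 2 is the protocol's only statistical calculation. Exact (Clopper-Pearson) two-sided 95% binomial intervals reproduce all 20 cells to one decimal. At n = 5,000 and 5% the interval is 4.41 to 5.64, printed as 4.4 to 5.6, so the half-width is (5.64 − 4.41)/2 ≈ 0.6 points.

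**2. What incomplete capture does.** Let p be the true proportion with a contraindication and s the fraction of those users whose contraindication is recorded. With no false positives, observed proportion = p × s. The documents give neither p nor s, so both are assumptions. For p = 5% and n = 5,000:

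| Assumed capture s | Observed (5% × s) | 95% CI | Shift from 5% |
|---|---|---|---|
| 0.9 | 4.5% | 3.9 to 5.1 | 0.5 |
| 0.7 | 3.5% | 3.0 to 4.1 | 1.5 |
| 0.5 | 2.5% | 2.1 to 3.0 | 2.5 |
| 0.3 | 1.5% | 1.2 to 1.9 | 3.5 |

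The shift 5% × (1 − s) equals the 0.6-point half-width at s = 0.88. Below that capture, the error from what the database cannot see exceeds the sampling error that Table 2 presents as the study's precision.

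**3. The pooled contraindication component, if it is pooled at all.** The weights are not stated. Assume a true 5% everywhere, s = 0.5 in France and full capture elsewhere:
- equal weights: (5 + 5 + 2.5)/3 = 4.2%;
- weights 8:15:4, from the Table 1 user estimates: (8 × 5 + 15 × 5 + 4 × 2.5)/27 = 125/27 = 4.6%.

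These are figures for the contraindication component, not for total off-label use.

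**4. Direction for total off-label use.** The same gap in Cegedim works both ways:
- It hides contraindications, which lowers any off-label figure that includes them.
- It also hides evidence that supports on-label use: hip or knee replacement (Table 3), and prior stroke, systemic embolism or heart failure (Table 4). Missing a joint replacement can turn an on-label user into an apparent off-label one. Missing a risk factor can do so under the restrictive definition in 3.5.1.

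The documents give nothing with which to weigh one effect against the other.

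**The case against.** **The limitation is disclosed, and results are given by database.** Section 4 warns that comorbidity information may be missing or poor in some databases, 3.6.1 assesses conditions as available, and 3.1.2 names the lack of hospitalisation data. Results are shown per database, with France split by panel. The problem is therefore not hidden. But the warning does not mention contraindications or the direction of the error, and it changes no analysis. Reporting by database displays the artefact as a country difference and does not remove it.

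**The detail belongs in the database-specific protocols.** This is fair for code lists and algorithms. Whether contraindications are part of the main and pooled outcome is a common-protocol matter, and there 3.5.2 and 3.7.1 disagree. The Appendix 4 diagram may bear on this, but its content is not available here.

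**Some contraindications will be seen in Cegedim.** This stands. The database holds medical history and outpatient diagnoses, and a panel cardiologist who prescribes both drugs is captured. Capture is incomplete, not nil.

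A reader might also infer three stronger conclusions that the documents do not support:
- *CPRD under-reports as well.* Partial HES linkage alone does not show this, because GPs record hospital diagnoses and letters and free text exist.
- *French total or pooled off-label use is too low.* The net direction is open (step 4 of the working).
- *The pooled figure certainly contains contraindications.* The pooling sentence speaks only of off-label use, which 3.5.2 defines by indication.

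Nor is Denmark a perfect reference for every item. Conditions managed only in general practice depend on DAMD, so what can be observed varies by contraindication as well as by country.

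**Conclusion.** The point holds in a limited form. For contraindications that depend on hospital records or on another prescriber's records, the Cegedim proportions are biased downward relative to Denmark. So is the contraindication component of any off-label figure that includes them. This follows from the protocol's description of its databases and rests on one assumption: that panel physicians do not re-enter every such event or drug.

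The size is unknown. The table in the working illustrates it under assumed values and does not estimate it; it shows only that moderate under-capture would outweigh the stated precision. Nothing firmer can be said about CPRD or about total French or pooled off-label use. This is an inexpensive correction to definition and reporting, worth making before the database-specific protocols are final. It does not undermine the study.

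**What to change.** 1. Reconcile 3.5.2 with 3.7.1 (and 3.5.1), so that the protocol says once whether, and at which level of the definition, contraindications count toward off-label use.
2. Report main and pooled off-label prevalence twice, by indication only and with contraindications added, using the same definition in all three databases. Removing the affected contraindications from the French figure alone would discard the cases that were captured and give France a different outcome.
3. In Cegedim, mark hospital-dependent and other-prescriber contraindications as *recorded by the panel physician only*, and state that they are not comparable with the Danish prevalence.
4. In CPRD, add the contraindication estimate among HES-linked users as a sensitivity analysis. Comparing it with the estimate in all users gives some evidence on whether under-capture occurs there.

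The cost is protocol wording and a few table rows, using data and linkage already described. The HES-linked subset will have a wider interval. If, for example, 2,000 of 5,000 CPRD users were linked (an assumption), Table 2 gives 4.1 to 6.0 in place of 4.4 to 5.6 at 5%.

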Anticoagulation for patients with heart valve replacement or a stent	Heart valve replacement Insertion of coronary stent, bypass anastomosis for heart revascularisation	See codes in Table 4 Z95.1 Z95.5	For stent or aorto-coronary bypass surgery in absence of atrial fibrillation (see Table 4)
General prophylaxis or treatment of a thrombus in any site	Malignancies	C00-C97	In absence of codes in Table 3 or Table 4
Patients with hypercoagulability	Antiphospholipid syndrome	D68.61	In absence of codes in Table 3 or Table 4

* = wild card character indicating additional subcodes under this primary code; ICD-10-CM = International Statistical Classification of Diseases and Related Health Problems, 10th Revision, Clinical Modification, 2014 version. Procedural codes will be refined based on the dictionary system in place in each database

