3.6.1 Assessment of clinical history and comorbidities

The presence of the following diseases and conditions of interest will be assessed based on the total cumulative clinical history or the baseline period for each patient at the index date, as available in each database:

- Chronic diseases, particularly those related to atrial fibrillation, including cardiovascular and cerebrovascular diseases, hypertension, and diabetes mellitus.
- Diseases or conditions related to the potential off-label use of dabigatran etexilate such as other heart valve replacement, deep venous thrombosis, pulmonary embolism, and disorders of coagulation (i.e., antiphospholipid syndrome).
- Surgical or percutaneous procedures related to the potential off-label use of dabigatran etexilate such as coronary revascularisation procedures or surgery, general or orthopaedic surgery other than hip and knee orthopaedic surgery. The presence of lower limb fractures will also be evaluated.

A complete list of comorbidities will be developed and included in the detailed, database-specific study protocol.

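### Two rows of Table 5 do not code the off-label categories they are meant to identify, and their absence condition is wider than it needs to be

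*Protocol*

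**What the plan says.** Section 3.5.2 names five potential off-label categories, states that the list is not exhaustive, and continues: "A preliminary list of ICD-10-CM codes to identify these conditions is provided in" Table 5. Two of the five matter here.

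- **Thrombus at any site.** The category is "General prophylaxis or treatment of a thrombus in any site". In Table 5 its only description is "Malignancies" and its only code range is C00-C97.
- **Hypercoagulability.** The text reads "Patients with hypercoagulability (e.g., factor V Leiden thrombophilia"). In Table 5 the only description is "Antiphospholipid syndrome" and the only code is D68.61, without the wildcard that the table uses elsewhere. Section 3.6.1 repeats the narrow form for covariates: "disorders of coagulation (i.e., antiphospholipid syndrome").

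Both rows apply only "In absence of codes in Table 3 or Table 4". Table 5 has a separate row for treatment or secondary prevention of venous thromboembolism (VTE), with the codes "I80.1*, I80.2*, I82.3* I26" (and subcodes). Arterial embolism and thrombosis (`I74*`) appears only in Table 4, as a secondary code supporting the atrial fibrillation (AF) indication.

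The table is labelled preliminary. The final lists and proxy algorithms are left to the database-specific protocols, which Section 3 says are to be based on this one.

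**The concern.** A code list should find the condition named in its row. Here one row names thrombus prophylaxis or treatment and lists cancer. The other names hypercoagulability and lists one acquired disorder, leaving out the text's own example.

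Section 3.7.1 makes the proportion of each of the most common off-label indications part of the main analysis, so these rows feed a stated output. They matter most in Denmark, where Table 1 and Section 3.3.5 say that indication is inferred from proxies. If the three database teams each repair the table in their own way, the breakdowns may also stop being comparable across countries, although the protocol wants extraction and analysis standardised as far as possible.

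**Working it through.** The protocol states no figure for this point, so the check sets the text against the tables.

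**Step 1: categories against codes.**

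| Section 3.5.2 category (short form) | Table 5 codes | Do the codes identify it? |
|---|---|---|
| DVT/PE treatment and recurrence | `I80.1*`, `I80.2*`, `I82.3*`, `I26*` | Thrombosis codes present |
| Prophylaxis outside hip/knee surgery | `S80*`-`S89*`, `S72*` | Proxy for prophylaxis |
| Valve replacement or stent | Table 4 valve codes, Z95.1, Z95.5 | Condition present |
| Thrombus at any site, prophylaxis or treatment | C00-C97 | No thrombosis or embolism code |
| Hypercoagulability | D68.61 | Text's example not covered |

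**Step 2: trace users through the rows as printed.** None of these users has AF or a joint replacement.

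- *Thrombus at a site outside the VTE row, no cancer:* no Table 5 row applies.
- *Arterial embolism (`I74*`), no cancer:* the only matching code is in Table 4 as support for AF, so no Table 5 row applies.
- *Cancer, no thrombosis code, no Table 3 or 4 code:* enters the any-site row, which cannot separate possible prophylaxis from treatment of a thrombus.
- *Factor V Leiden only:* no Table 5 row applies.
- *Antiphospholipid syndrome plus hypertension:* has the row's own code, but hypertension (`I10*`-`I15*`) is a Table 4 code, so the literal condition removes the user.

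**Step 3: reach of the absence condition.** Table 4 holds the primary code `I48*`, the valve exclusion codes, and secondary codes for stroke/TIA, heart failure, systemic embolism (`I74*`), diabetes, hypertension and ischaemic heart disease. A secondary code without `I48*` gives no on-label indication, yet read literally it blocks both rows. The stent entry in the same table uses a narrower condition, absence of AF, so the wide wording was not the only form available. As printed, `I74*` can keep a user out of the any-site row only if that user also has cancer. Once `I74*` is added to the row, however, the literal condition would forbid the code that the row requires, so the two changes must be made together.

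**Step 4: effect on the estimates.** The document does not say plainly whether off-label is the residual after on-label codes or needs a positive off-label code.

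- *Residual:* the overall proportion is unchanged and only the breakdown is wrong.
- *Positive code required:* observed proportion = true proportion × (1 − share missed). As an illustration only, take Table 2's case of 5% in 5,000 (250 users; the exact binomial interval reproduces the printed 4.4% to 5.6%). Assumed missed shares of 5%, 10%, 20% and 30% give about 4.8%, 4.5%, 4.0% and 3.5%. At 20%, 200/5,000 = 4.0%, with interval 3.5% to 4.6%. The shares are assumptions; the protocol gives none.

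**The case against.** The best defence is that the table is a starting point. It is called preliminary, and the final codes and algorithms belong to later documents. That lowers the severity but does not remove the point, because those documents are to be built on this protocol, and a row that pairs one concept with codes for another is a mismatch and not just an incomplete list.

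Three stronger readings are tempting, and the documents do not support them.

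- *The main outcome is biased.* Section 3.5.2 defines off-label use as use for something other than the labelled indications, which points to a residual definition. On that reading the overall proportion does not move.
- *Every user with a thrombus elsewhere or an inherited thrombophilia is missed.* Codes are not the only route to indication. Section 3.3.5 says that CPRD usually records the indication at a first GP prescription, and that Cegedim attaches a diagnosis (which Section 3.1.2 says need not be the indication). Section 3.3.5.1 plans manual review of at least 200 CPRD profiles to validate the algorithms. That review covers CPRD only, so Denmark stays the most exposed.
- *Cancer patients in the any-site row are false cases.* The row includes prophylaxis, which needs no thrombosis code. Cancer is a possible, if crude, proxy for that half.

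It is also fair to say that only the most common off-label indications are promised, and nothing shows that the affected conditions rank among them.

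**Conclusion.** The mismatch stands on the face of the protocol. Malignancy codes cannot identify treatment of a thrombus outside the VTE row, the hypercoagulability row omits factor V Leiden, and the absence condition read literally drops users who have no on-label indication.

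The supported consequence is misclassification within the breakdown of off-label indications, mainly where indication rests on code proxies. The overall off-label proportion is affected only if a positive Table 5 code is required. The Appendix 4 diagram may settle that, but it was not readable in the text reviewed.

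The size cannot be estimated. It would need the share of off-label users with cancer, thrombophilia or other-site thrombus and the relevant absence or presence of Table 3 and 4 codes, and the protocol gives none of these. A reader might assume a cancer share and derive a count of mislabelled users, but the count would be no better than the assumption.

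**What to change.** Before the database-specific protocols are finalised:

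1. Add thrombosis and embolism codes outside the VTE row to the any-site row, including `I74*` when `I48*` is absent.
2. Report C00-C97 without a thrombosis code in its own row, as possible cancer-associated prophylaxis.
3. Extend the hypercoagulability row, and the matching item in Section 3.6.1, to factor V Leiden and other thrombophilias.
4. Limit the absence condition in these rows to the primary on-label codes: `Z96.64*`, `Z96.65*` and `I48*`, with their procedural equivalents in each database.
5. Carry the changes into the Read and ICPC lists.

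Two sentences should go with the table. One should say whether off-label status is the residual or needs a positive code. The other should say whether a user may count in more than one Table 5 row, since item 4 lets a user with thrombophilia and a DVT code meet two.

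The cost is an edit to a preliminary code table and a line in Section 3.6.1. No new data, sample size or analysis is needed.
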